All	
 • Minor administrative updates 	
 • Administrative/improve clarity
Section 1.2	
 • Updated schema to reflect all protocol v2.00 changes • Moved schedule of activities (SoA) to section 8.1.1 	
 • Administrative/improve clarity
Section 3	
 • Separated phase 2b and phase 3 safety objectives in the table 	
 • Administrative/improve clarity
Section 6.3	
 • Updated blinding information (participants and CEC will be blinded) 	
 • Consistency throughout protocol

Section 8.1.1	
 • SoA moved here and updated 	
 • Consistency with protocol v2.00 changes and improve clarity
Section 8.1.2	
 • Section added 	
 • Clarify laboratory samples and values from SoA
Section 8.1.3	
 • Section added 	
 • Elaborate on SoA
Section 8.2	
 • Clarification around clinical events and efficacy outcomes 	
 • Administrative/improve clarity
Section 10.1.5	
 • Section added 	
 • Clarify study committees

 • Protocol V4.00 28Oct2020 		
Throughout	
 • Changed “coagulation and inflammatory biomarkers” to “biomarkers associated with outcomes including those related to coagulation and inflammation” 	
 • Clarity
Throughout	
 • Administrative updates 	
 • Consistency and clarity
4.1 & 9.4.2	
 • Stratification changed from “ongoing treatment with remdesivir and other agents with demonstrated efficacy in patients with COVID-19” to “participant’s local laboratory D-dimer level at screening” 	
 • Removed as agents with demonstrated efficacy have become standard of care. D-dimer reflects disease severity
4.3 & 6.3	
 • Removed clinical sites will be designated as prophylactic or therapeutic 	
 • Reflects evolution of standard of care
5.1	
 • Inclusion criterion 7 • Exclusion criterion 2 • Exclusion criterion 3 	
 • Align language with intent
6.2.4	
 • Storage of prepared syringes of rNAPc2 updated. 	
 • Clarity
6.3	
 • Site-based randomization 	
 • Clarity
8.1.1 & 8.1.3	
 • Schedule of Activities (SoA) and visit descriptions updated to reflect daily clinical assessments 	
 • Clarity
8.1.2	
 • Record local laboratory values for troponin, brain natriuretic peptide (BNP) and NT-proBNP 	
 • Capture cardiac biomarkers
8.1.3	
 • Demographics moved to Screening visit; sex, childbearing potential, and race added 	
 • Capture demographics for all screened participants

8.2	
 Section re-arranged 	
 Clarity & consistency
9.4.3	
 Analysis method for proportion of participants alive and out of the hospital at 30 days post-randomization added 	
 Clarity
9.4.6	
 Alpha level for final analysis added 	
 Clarity
9.4.8	
 Executive Committee (EC) Chair or representative will be a member of the Unblinded Review Committee (URC) 	
 Consistent with Data Safety Monitoring Committee charter
10.1.5	
 DSMC unscheduled meetings and real-time notification for severe safety events 	
 Safety

 Protocol V5.00 01Feb2021 		
Throughout	
 Revision of primary efficacy endpoint to change in D-dimer from baseline to Day 8 or day of discharge, if discharge prior to Day 8 	
 Change based on additional clinical information for duration of hospitalization in COVID-19 patients.
Throughout	
 Revision of primary safety endpoint to major or non-major clinically relevant bleeding within 8 days of randomization 	
 Changed to facilitate a more accurate assessment of bleeding events between rNAPc2 and heparin
5.3 & 8.1.2	
 Revised to require negative pregnancy test for women of childbearing potential and clarification of effective contraception during the study 	
 Health Regulatory agency feedback
8.1	
 Visits and central lab assessments revised to align with endpoints: add Day 2; change Day 8 to Day 8 or day of discharge, if discharge prior to Day 8; remove Day 10 	
 Changed based on additional clinical information for duration of hospitalization in COVID-19 patients
6.1.2	
 Add clarification for standard of care thromboprophylaxis when fewer than 3 doses of rNAPc2 are prescribed (if patient is discharged prior to Day 5). 	
 Safety
6.5	
 Clarification to prohibited concomitant medication use during 	
 Safety

	trial and concurrently with study drug administration.	
8.4.5	
 Clarify AE/SAE reporting requirements, especially as related to expedited reporting 	
 Safety
Throughout	
 Administrative updates throughout, including incorporation of appendices 	
 Clarity and consistency

 Protocol V6.00 07Jul2021 		
Throughout	
 Administrative updates 	
 Consistency and clarity
4.3	
 Justification for dose 	
 Justification was expanded for clarity and to include additional detail from prior investigations
5.0	
 Inclusion/Exclusion criteria clarifications 	
 In agreement with regulatory agency requests, some inclusion/exclusion criteria were revised to include additional details/clarification while preserving the intention of each modified criterion
5.1 & 5.3	
 Added language requiring male patients to avoid partner pregnancy and sperm donation 	
 In agreement with regulatory agency request
8.1.2	
 Removed central laboratory assessment of AST, ALT and bilirubin 	
 Remove duplication of laboratory assessments in line with standard of care site COVID-19 practices
8.5	
 Removed Unanticipated Problem Section and Unanticipated Problem Reporting Section 	
 These sections did not inform clinical trial execution for ASPEN-COVID-19
9.0	
 Increase to study sample size Addition of an interim efficacy analysis and removal of Unblinded Review Committee Clarification that primary endpoint analysis will evaluate proportional changes in D-dimer at Day 8; to be detailed in the statistical analysis plan 	
 Given the evolution of COVID-19 management since the start of ASPEN-COVID-19, the original rNAPc2 sample size and treatment effect assumptions were updated in order to increase experience in a diversity of COVID-19 patients. Changes in COVID-19 management that were considered include 1) evolving evidence for standard of care, 2) widespread use of several COVID-19 therapies of proven

		benefit, and 3) changes in background therapy.
--	--	--

Protocol Amendment History

Version	Date	Description of Change	Brief Rationale
2.00	28Aug2020	Design adjustments prior to study initiation	Incorporate feedback
3.00	16Sep2020	Administrative adjustments prior to study initiation	Ensure consistency and clarity throughout the protocol
4.00	28Oct2020	Adjustments prior to study initiation	Incorporate feedback
5.00	01Feb2021	Update to endpoints and revision of laboratory assessments; Clarification on requirements for women of child-bearing potential and safety reporting	Scientific revision of endpoints; safety clarifications
6.00	07Jul2021	Clarification of some inclusion/exclusion based on regulatory agency review; increase of study sample size	Given the evolution of COVID-19 management since the start of ASPEN-COVID-19, the original rNAPc2 sample size and treatment effect assumptions were updated in order to increase experience in a diversity of COVID-19 patients

Protocol Approval Signature:

10.4 Post-COVID Functional Status Scale60

11 REFERENCES64

STATEMENT OF COMPLIANCE

This study will be conducted in compliance with Good Clinical Practice (GCP) and applicable regulatory requirements.

STUDY ADMINISTRATION

Principal Investigator	Sponsor representatives
[name], MPH Professor of Medicine, University of Colorado Executive Director, Colorado Prevention Center	[name], PhD Chief Executive Officer, ARCA biopharma Professor of Medicine, University of Colorado
[name]	[name] Chief Medical Officer, ARCA biopharma
[contact]	ARCA biopharma, Inc. [name] [contact]

1 PROTOCOL SUMMARY**1.1 SYNOPSIS****Title:**

Assessing Safety, Hospitalization and Efficacy of rNAPc2 in COVID-19 (ASPEN-COVID-19)

Study Description:

This protocol describes sequential randomized, multicenter, active comparator studies evaluating the hypothesis that rNAPc2, a novel, potent and highly selective tissue factor inhibitor with anticoagulant, anti-inflammatory and potential antiviral properties, shortens time to recovery compared to heparin in hospitalized patients with COVID-19 and elevated D-dimer levels. The study utilizes a PROBE (Prospective Randomized Open-label, Blinded End-point) design. Study participants and Clinical Endpoint Committee (CEC) members assessing the clinical endpoints will be blinded to treatment assignment. The protocol comprises sequential Phase 2b and Phase 3 studies. Analysis of Phase 2b data could lead to study discontinuation, adjustment of eligibility criteria or sample size, and will inform the rNAPc2 dose regimen to be studied in Phase 3.

Objectives:

Phase 2b: The primary safety and efficacy objectives are to identify an rNAPc2 dosing regimen with an acceptable bleeding profile and which reduces D-dimer levels compared to standard of care (SoC) heparin regimens. Secondary and exploratory objectives are to compare the treatment groups in terms of biomarkers associated with outcomes including those related to coagulation and inflammation, as well as clinical and functional outcomes that will also be assessed during Phase 3.

Phase 3: The primary safety and efficacy objectives are to assess major or

non-major clinically relevant bleeding and whether rNAPc2 reduces time to recovery relative to heparin. Secondary and exploratory objectives are to compare the treatment groups in terms of a composite of thrombotic events and all-cause mortality; thrombotic events; all-cause mortality; biomarkers associated with outcomes including those related to coagulation and inflammation; health resource utilization; and post-COVID-19 functional status.

Endpoints:**Phase 2b**

Primary efficacy endpoint: change in D-dimer level from Baseline to Day 8, or day of discharge if prior to Day 8.

Primary safety endpoint: major or non-major clinically relevant bleeding within eight (8) days of randomization as compared to heparin.

Secondary and exploratory efficacy endpoints: change in D-dimer level from baseline to 24h post-dose (Day 2) and Day 3, change in biomarkers associated with outcomes including those related to coagulation and inflammation from baseline through Day 8; other clinical and functional outcomes, including time to recovery as measured by the 8-point Adaptive COVID-19 Treatment Trial (ACTT) scale.

Secondary safety endpoints: major or non-major clinically relevant bleeding with rNAPc2 vs. heparin, bleeding with higher vs. lower dose rNAPc2 through Day 30, and other adverse events (AEs).

Phase 3

Primary efficacy endpoint: time to recovery within thirty (30) days of randomization using the ACTT ordinal scale.

Primary safety endpoint: major or non-major clinically relevant bleeding within eight (8) days of randomization as compared to heparin.

[figure not shown]
[figure not shown]
Secondary and exploratory efficacy endpoints: time to first occurrence of a composite of thrombotic events and all-cause mortality within thirty (30) days of randomization; time to first occurrence of thrombotic events within 30 days of randomization; time to all-cause mortality within thirty (30) days of randomization; change in biomarkers associated with outcomes including those related to coagulation and inflammation from Baseline through Day 8; proportion alive and out of hospital at thirty (30) days post-randomization; days in intensive care unit, on ventilator, vasopressors, renal replacement therapy, and circulatory support; Post-COVID Functional Status (PCFS) score at discharge and Day 30.

Secondary safety endpoints: major or non-major clinically relevant bleeding with rNAPc2 or heparin, and other AEs.

Study Population:	
Phase 2b: Approximately 160 men or women enrolled at approximately 20 sites, 18 to 90 years of age with COVID-19 documented by a validated test such as polymerase chain reaction (PCR) within one (1) week of hospitalization or screening and D-dimer above the upper limit of normal.
 
Phase 3: Approximately 450 additional participants (same criteria as listed for Phase 2b) at up to approximately 80 sites.

Phase:	2b/3
Description of Sites/Facilities Enrolling Participants:	Approximately 80 global clinical sites (in total between Phases 2b and 3) will be selected based on prior performance in randomized clinical trials and access to patients with COVID-19.
Description of Study Intervention:	
Phase 2b: Participants will be randomly assigned 1:1:2 to receive rNAPc2 at 1 of 2 dose regimens, or a heparin regimen per site SoC (prophylactic or therapeutic). The higher rNAPc2 dose regimen will include a 7.5 µg/kg subcutaneous (SC) loading dose on Day 1 followed by 5µg/kg SC on Days 3 and 5; the lower dose regimen will be administered as a 5 µg/kg SC loading dose on Day 1 followed by 3µg/kg SC on Days 3 and 5. Prophylactic or therapeutic doses of low molecular weight heparin (LMWH) or unfractionated heparin (UFH) will be administered according to local SoC in the control group. Participants will be stratified by local laboratory D-dimer level at screening.
 
Phase 3: Participants will be randomly assigned to receive rNAPc2 at a dose regimen selected based on Phase 2b data or to heparin (1:1).

Participant Duration:	Up to 40 days

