8 STUDY ASSESSMENTS AND PROCEDURES

8.1 STUDY PROCEDURES

8.1.1 SCHEDULE OF ACTIVITIES

Table 2a. Schedule of Activities (SoA)

Activity	Screen Day -7 to 1	Baseline Day 1	Day 2 (24h post-dose \pm 2h)	Day 3 \pm 1d	Day 5 \pm 1d	Day 8 \pm 1d	Day of Hospital Discharge	Day 30 \pm 3d
Informed consent	x							
Assess eligibility	x	x						
Randomize		x						
Medical history (COVID-19, cardiovascular, medical/ surgical history) ^b		x						
Concomitant medication ^b		x	x	x	x	x	x	x ^d
Baseline demographics ^b	x							
Focused physical examination, vital signs, weight, height ^b		x						
Study medication ^c		rNAPc2 7.5 μ g/kg SC on Day 1 and 5 μ g/kg SC on Days 3 and 5 or rNAPc2 5 μ g/kg SC on Day 1 and 3 μ g/kg SC on Days 3 and 5 or heparin per SoC						
Local laboratory values	x ^a	Record values of interest performed in the hospital clinical laboratory until hospital discharge or day 30 visit (whichever is first). In the case where a lab test is measured multiple times per day, the first scheduled values as well as any additional values that represent a clinically significant change should be reported.						
Assess need for inpatient medical services & complete ACTT			Daily until discharged to outpatient status or death or Day 30 reached					
Clinical & adverse events ^g	x	x	x	x	x	x	x	x ^d
Post-COVID functional status (PCFS) scale							x ^h	x ^d
Vital status								x ^d
Healthcare utilization							x	x ^d
Central Laboratory assessments (see Table 2b)		x	x	x ^e		x ^f	x ^f	x ^e

^a Local lab D-dimer drawn during hospitalization and prior to randomization will be used for eligibility and randomization stratification

^b May be obtained/extracted from medical record to minimize staff exposure to COVID-19

^c rNAPc2 must be dosed on Days 1, 3 and 5; only one rNAPc2 dose regimen is anticipated in Phase 3; Participants randomized to receive heparin will have doses administered per standard of care (SoC)

^d Participants who are discharged prior to Day 30 may have these activities performed remotely

^e For phase 2b only

^f If participant is discharged prior to Day 8, central laboratory assessments should be performed at hospital discharge

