The following procedures will occur during the Day 5 visit:

- Concomitant medication (may be obtained/extracted from the medical record to minimize staff exposure to COVID-19)
- Study medication administration
 - If an rNAPc2-allocated participant is discharged from the hospital before receiving the Day 5 dose, the dose(s) should be recorded in the electronic Case Report Form (eCRF) as not administered.
- Local laboratory values, if applicable
- Assess the need for inpatient medical services and complete ACTT
 - The need for inpatient medical services should be assessed daily after randomization until the participant is discharged from the hospital, deceased, or Day 30 visit is reached.
 - Documentation pertaining to this assessment must be provided to the CEC as outlined in the Site Manual.
- Clinical events and adverse events assessment
 - Assess for the occurrence of any adverse events and report via the eCRF as appropriate. See [Section 8.4 Adverse Events and Serious Adverse Events](#) for more information about adverse events.
 - Assess for the occurrence of any clinical event that suggests the possibility that an efficacy outcome event has occurred. See [Section 8.2 Efficacy Assessments](#) for more information about clinical events of interest.

Day 8 Visit (+/- 1 Day)

The following procedures will occur during the Day 8 visit:

- Concomitant medication (may be obtained/extracted from the medical record to minimize staff exposure to COVID-19)
- Study medication administration, if randomized to heparin and still hospitalized
- Local laboratory values, if applicable
- Assess need for inpatient medical services and complete ACTT
 - The need for inpatient medical services should be assessed daily after randomization until the participant is discharged from the hospital, deceased, or Day 30 visit is reached.
 - Documentation pertaining to this assessment must be provided to the CEC as outlined in the Site Manual.
- Clinical events and adverse events assessment
 - Assess for the occurrence of any adverse events and report via the eCRF as appropriate. See [Section 8.4 Adverse Events and Serious Adverse Events](#) for more information about adverse events.
 - Assess for the occurrence of any clinical event that suggests the possibility that an efficacy outcome event has occurred. See [Section 8.2 Efficacy Assessments](#) for more information about clinical events of interest.

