8.3 SAFETY AND OTHER ASSESSMENTS

Safety assessments will include monitoring of serious and non-serious AEs and study endpoints. Efficacy and safety endpoints, including all bleeding events, will not be considered as AEs or SAEs (see [Section 8.4 Adverse Events and Serious Adverse Events](#)). Safety evaluations will be assessed by the investigator per the SoA via EMR review, telephone or web contact with the participant or their health care provider.

Safety Events:

Bleeding events are considered safety endpoints for the study.

The study will classify bleeding events as major, non-major clinically relevant or non-major non-clinically relevant. Safety endpoints for this study include major, critical site and fatal bleeding and non-major clinically relevant bleeding using modified International Society on Thrombosis and Haemostasis (ISTH) bleeding criteria. All bleeding events will be assessed, classified and reported by the investigator in the eCRF. Major bleeding events will be adjudicated by the CEC.

An ISTH major bleeding event is defined as overt bleeding that is associated with:

- A fall in hemoglobin of 2 g/dL (1.24 mmol/L) or more, or
- A transfusion of 2 or more units of packed red blood cells or whole blood, or
- A critical site: intracranial, intraspinal, intraocular, pericardial, intra-articular, intramuscular with compartment syndrome, retroperitoneal, or
- A fatal outcome.

Non-major clinically relevant bleeding is defined as overt bleeding not meeting the criteria for major bleeding but associated with medical intervention, unscheduled visit or telephone call with a healthcare provider or temporary or permanent cessation of study treatment or associated with discomfort for the participant such as pain or impairment of activities of daily life.

Bleeding events not meeting the definition of major or non-major clinically relevant bleeding will be classified as non-major, non-clinically relevant.

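### After the last rNAPc2 dose, only participants still on heparin can meet the treatment-cessation criterion for clinically relevant bleeding, so identical late bleeds can be counted differently by arm

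*Protocol*

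**What the plan says.** Protocol 1.1 and Section 3 define the primary safety endpoint in both phases as "major or non-major clinically relevant bleeding within eight (8) days of randomization as compared to heparin". SAP 2.4.2 repeats it, and SAP 8.2.1 extends the same bleeding category to Day 30.

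Protocol 8.3 defines a non-major clinically relevant bleed as an overt, non-major bleed that meets at least one of these alternatives:

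- it is "associated with medical intervention, unscheduled visit or telephone call with a healthcare provider";
- it leads to "temporary or permanent cessation of study treatment";
- it is "associated with discomfort for the participant such as pain or impairment of activities of daily life".

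What is left over falls outside the endpoint: "Bleeding events not meeting the definition of major or non-major clinically relevant bleeding will be classified as non-major, non-clinically relevant".

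The two arms have different treatment periods. Footnote c of the Schedule of Activities says "rNAPc2 must be dosed on Days 1, 3 and 5", and the Day 5 visit has a window of ±1 day. For heparin, the Day 8 and Day 30 visit descriptions in Protocol 8.1.3 both list "Study medication administration, if randomized to heparin and still hospitalized". The SAP 5.2 per-protocol definition likewise sets three rNAPc2 doses against standard-of-care drug through Day 7.

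**The concern.** Two of the three kinds of criterion (intervention or contact, and discomfort or impairment) are open to every participant on every day. The cessation criterion is not. Once the last rNAPc2 dose has been given, there is no study treatment left to hold or stop in that arm, while a participant still on heparin has a dose that can be held. The same minor bleed on Day 7 can then be clinically relevant in one arm and not in the other.

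The endpoint is explicitly comparative and supports the judgement that an rNAPc2 regimen has an acceptable bleeding profile. Phase 3 uses it again. Neither document limits the cessation criterion to the period when both arms are being dosed, or otherwise removes the difference.

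**Working it through.** **1. Are the late days still a time of rNAPc2 effect?** Protocol 6.5.1 gives a half-life of about 72 hours after the Day 5 dose, so on Day 8 the drug is only about one half-life past its last dose. SAP 5.2 runs the on-treatment scope to 72 hours after permanent discontinuation. With a Day 5 last dose, bleeds on Days 6 to 8 are therefore in scope for rNAPc2 but cannot qualify through cessation.

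**2. Does later anticoagulation restore the criterion?** Protocol 6.1.2 allows hospitalized rNAPc2 participants standard-of-care thromboprophylaxis from Day 8 if clinically indicated. The documents do not call this study treatment. On a plain reading, holding it after a bleed on Day 10 would not meet the criterion, while holding heparin in the control arm would.

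**3. Share of the window affected.** L = (8 − day of last dose) / 8.

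- Day 5: 3/8 = 37.5%
- Day 4: 4/8 = 50%
- Day 6: 2/8 = 25%

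**4. Size.** The documents give no bleeding rate, margin or power for this endpoint, so there is no stated figure to reproduce. The following are assumptions:

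- b: 8-day rate of non-major clinically relevant bleeding if dosing continued, equal in both arms;
- f: share of those bleeds that qualify only through cessation;
- bleeds are spread evenly over the 8 days;
- every heparin participant is dosed through Day 8.

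Spurious difference = b × L × f. Spurious risk ratio = 1 − L × f. Phase 2b has about 160 participants randomized 1:1:2, so about 80 on pooled rNAPc2 and 80 on heparin. With L = 0.375:

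| b | f | Heparin | rNAPc2 | Events lost per 80 | Risk ratio |
|---|---|---|---|---|---|
| 5% | 10% | 5.0% | 4.8% | 0.05 × 0.375 × 0.10 × 80 = 0.15 | 0.96 |
| 10% | 30% | 10.0% | 8.9% | 0.10 × 0.375 × 0.30 × 80 = 0.9 | 0.89 |
| 20% | 50% | 20.0% | 16.3% | 0.20 × 0.375 × 0.50 × 80 = 3.0 | 0.81 |

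With a last dose on Day 4 or Day 6, the ratio at f = 50% becomes 0.75 or 0.875; at f = 10% it is 0.95 or 0.975.

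**5. What shrinks it.** If only a share p of the late bleeds in the heparin arm occur while heparin is still being given, the difference becomes b × L × f × p. For example, p = 0.5 (assumed) turns the middle row into 0.45 events per 80. Major bleeds are counted alike in both arms. Adding them leaves the absolute difference unchanged and brings the ratio for the full endpoint closer to 1.

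**6. Day 30.** At most 25 of 30 days (83.3%) follow a Day 5 last dose. The ratio 1 − 0.833 × f is then 0.92, 0.75 and 0.58 for f = 10%, 30% and 50%. This is a bound: it needs every heparin participant to stay in hospital on heparin to Day 30.

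**The case against.** The case against rests on five points.

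- **Few bleeds are affected.** The other criteria are broad and joined by alternatives, so many bleeds that lead to a held dose will also qualify by another route. This stands, and it is why low values of f belong in the range. A reader might infer a much larger distortion. For example, cessation-only bleeds in 15% of participants on top of 5% other events would give (0.05 + 0.625 × 0.15) / 0.20 = 0.72. But that requires 0.15 / 0.20 = 75% of heparin-arm events to qualify solely through a held dose, and nothing in the documents supports such a share.
- **Many participants leave before Day 8.** The visit schedule expects this, and SAP 8.1 closes the window two days after an early discharge. This stands and reduces the effect. For the same reason, 25 of 30 days should not be read as the actual Day 30 gap.
- **The direction could be offset.** Protocol 6.5.1 gives half-lives of about 4½ hours for low molecular weight heparin and 1 hour for unfractionated heparin. When no dose can be withheld, a late rNAPc2 bleed might more often need active treatment, which counts as medical intervention. This is inference, but it means the direction should be stated as other things equal.
- **The endpoint is adjudicated.** A reader might infer that the bias comes from site investigators who know the assignment, because Protocol 8.3 has them classify all bleeds and names the Clinical Endpoint Committee (CEC) for major bleeds only. SAP 8.1 and 8.2.1, however, report these bleeds as adjudicated by the CEC, which is blinded, and Protocol 9.4.1 lets the SAP prevail on analysis. The two texts need reconciling. The asymmetry remains either way, because a blinded committee applying this definition would reproduce it.
- **Other summaries exist.** SAP 8.2.2 reports any bleeding through Day 8 and Day 30, so a reclassified bleed is still visible there. Major bleeding does not use the cessation criterion, and SAP 8.1 is descriptive, so no formal test is affected. These are real but partial safeguards. The any-bleeding table mixes in trivial bleeds, and the primary percentages would still be compared between arms.

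**Conclusion.** The plan as written counts one type of late bleed according to arm. Other things equal, this favours rNAPc2 in the Day 8 comparison and more so in the Day 30 comparison. It affects only bleeds that qualify solely through cessation, and only while the heparin participant is still receiving heparin.

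The size cannot be derived from the documents. For f of 10% to 50%, a Day 5 last dose and heparin through Day 8, the spurious risk ratio for non-major clinically relevant bleeding is about 0.96 to 0.81. With b of 5% to 20%, that is roughly 0.15 to 3 events per 80. Early discharge reduces these figures.

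A reader might conclude that the safety comparison is unusable or that the cessation criterion should be dropped. The documents support neither. The effect may be less than one event per arm, and a bleed that led to stopping rNAPc2 during Days 1 to 5 is a tolerability signal worth keeping. What is justified is a cheap parallel count that shows whether the definition matters.

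**What to change.** Keep the current endpoint and make these additions:

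1. On the eCRF and the adjudication form, record every criterion that each bleed met.
2. In SAP 8.1 and 8.2.1, pre-specify a parallel between-arm count of major or non-major clinically relevant bleeding that leaves out the cessation criterion.
3. Show cessation-only bleeds on a separate line by arm and by time: up to the last rNAPc2 dose versus after it, with the matching study days used for heparin.
4. Reconcile Protocol 8.3 with SAP 8.1 and 8.2.1 on who classifies non-major bleeds.

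The cost is one data field and one table; dosing and clinical management are untouched. The criterion has to be captured as events are reported, because it would be hard to reconstruct reliably afterwards. The parallel count omits early bleeds whose only consequence was a held dose, which is why it should sit beside the main count and not replace it.
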